Appendix 2. Schedule of Activities

Schedule of Activities, Protocol I1F-MC-RHBQ

CRF Visit (V) Number	Screening		Baseline Randomization	Blinded Treatment Period (Period 2)				
	V1		V2	V3	V4	V5	V6	V7
Weeks since Randomization			W0	W1	W2	W4	W8	W12
Study Days	-30 to -7 d	V1A: 2-3 d post-V1	1	7 ± 2d	14 ± 2d	28 ± 2d	56 ± 2d	84 ± 4d
Informed consent	X							
Complete medical history	X							
Demographics ^a	X							
Sociodemographics ^b			X					X
Physical examination ^c	X		X					X
Perianal/gluteal cleft characteristics examination	X		X					X
Inclusion/exclusion criteria ^d	X		X					
Body temperature			X					
Height			X					
Weight			X					X
Waist circumference			X					
Vital signs (BP and pulse)	X		X ^e	X	X	X	X	X ^e
Consumption habits ^f			X					
Concomitant medications	X		X	X	X	X	X	X
Review preexisting conditions/AEs			X	X	X	X	X	X
Randomization			X					
Administer IP on site			X					X

	Screening		Baseline Randomization	Blinded Treatment Dosing Period (Period 2)				
CRF Visit (V) Number	V1		V2	V3	V4	V5	V6	V7
Weeks since Randomization			W0	W1	W2	W4	W8	W12
Study Days	-30 to -7 d	V1A: 2-3 d post-V1	1	7 ± 2d	14 ± 2d	28 ± 2d	56 ± 2d	84 ± 4d
Dispense IP			X		X	X	X	X
Provide SDALg			X		X	X	X	X
Collect, review, and enter data from SDAL			X		X	X	X	X
Review e-diary				X	X	X	X	X
Dispense e-diary (includes GPSS, GPSIS, and SFQ)	X							
Collect e-diary								X
Clinical Efficacy/Health Outcomes								
sPGA (overall)	X		X	X	X	X	X	X
sPGA of Genitalia ^h	X		X	X	X	X	X	X
PASI (overall)	X		X	X	X	X	X	X
mGPASI ⁱ	X		X	X	X	X	X	X
BSA	X		X ^j	X	X	X ^j	X	X ^j
Fitzpatrick skin type			X					
GPSS ^k	Daily from Screening (V1) to Week 12 (V7)							X
GPSIS ^k	Weekly from Screening (V1) to Week 12 (V7)							X
SFQ ^k	Weekly from Screening (V1) to Week 12 (V7)							X
PatGA-Genital			X	X	X	X	X	X
Touch avoidance NRS			X		X	X	X	X

CRF Visit (V) Number	Screening		Baseline Randomization	Blinded Treatment Dosing Period (Period 2)				
	V1		V2	V3	V4	V5	V6	V7
Weeks since Randomization			W0	W1	W2	W4	W8	W12
Study Days	-30 to -7 d	V1A: 2-3 d post-V1	1	7 ± 2d	14 ± 2d	28 ± 2d	56 ± 2d	84 ± 4d
SF-36			X					X
DLQI			X		X	X	X	X
QIDS-SR16	X		X					X
C-SSRS [§]			X	X	X	X	X	X
Self-Harm Supplement Form [§]			X	X	X	X	X	X
CAPP (genital subindex)			X					X
Laboratory Tests								
Administer PPD/QuantiFERON [®] -TB Gold/T-SPOT [®] 1	X							
Read PPD		X						
Chest x-ray ^m	X							
ECG	X							
HIV/HCV	X							
HBV ⁿ	X		X					X
FSH ^o	X							
Serum pregnancy test ^p	X							
Urine pregnancy test ^q			X			X	X	X
Serum chemistry	X		X			X		X
Fasting Lipid panel ^r			X			X		X
Hematology	X		X			X		X
TSH and free T4	X							

CRF Visit (V) Number	Screening		Baseline Randomization	Blinded Treatment Dosing Period (Period 2)				
	V1		V2	V3	V4	V5	V6	V7
Weeks since Randomization			W0	W1	W2	W4	W8	W12
Study Days	-30 to -7 d	V1A: 2-3 d post-V1	1	7 ± 2d	14 ± 2d	28 ± 2d	56 ± 2d	84 ± 4d
Genetic biomarker exploratory storage samples (DNA) ^s			X ^t					
Nonpharmacogenetic biomarker exploratory storage samples (serum, plasma, mRNA) ^s			X		X	X		X
Immunogenicity testing ^{s,u}			X		X	X		X
PK sample (trough) ^{s,v}			X		X	X		X
Candida skin swab ^w			X					

	Open-Label Treatment (Period 3)					ETV	Post-Treatment Follow-Up (Period 4) ^x		
							Required Follow-Up Visits		As-Needed Follow-Up Visits
CRF Visit (V) Number	V8	V9	V10	V11	V12	ETVy	V801	V802	V803 ^z and onward
Weeks since Randomization	W16	W24	W28	W40	W52		LV + 4W	LV + 12W	LV + 24W
Study Days	112 ± 7d	168 ± 7d	196 ± 7d	280 ± 7d	364 ± 7d				
Sociodemographics ^b					X	X			
Physical examination ^c		X		X	X	X			
Perianal/gluteal cleft characteristics examination		X			X	X			
Weight					X	X			
Waist circumference					X	X			
Vital signs (BP and pulse)	X	X	X	X	X	X	X	X	X
Concomitant medications	X	X	X	X	X	X	X	X	X
Review preexisting conditions /AEs	X	X	X	X	X	X	X	X	X
Dispense IP	X	X	X	X					
Provide SDAL ^g	X	X	X	X					
Collect, review, and enter data from SDAL	X	X	X	X	X	X			

	Open-Label Treatment (Period 3)					ETV	Post-Treatment Follow-Up (Period 4) ^x		
							Required Follow-Up Visits		As-Needed Follow-Up Visits
CRF Visit (V) Number	V8	V9	V10	V11	V12	ETVY	V801	V802	V803 ^z and onward
Weeks since Randomization	W16	W24	W28	W40	W52		LV + 4W	LV + 12W	LV + 24W
Study Days	112 ± 7d	168 ± 7d	196 ± 7d	280 ± 7d	364 ± 7d				
Review e-diary						X			
Collect e-diary						X			
Clinical Efficacy/Health Outcomes									
sPGA (overall)	X	X	X	X	X	X			
sPGA of Genitalia ^h	X	X	X	X	X	X			
PASI (overall)	X	X	X	X	X	X			
mGPASI ⁱ	X	X	X	X	X	X			
BSA	X	X ^j	X	X	X ^j	X ^j			
GPSS ^k	X	X	X	X	X	X			
GPSIS ^k	X	X	X	X	X	X			
SFQ ^k	X	X	X	X	X	X			
Touch avoidance NRS	X	X	X	X	X	X			
SF-36					X	X			
PatGA-Genital	X	X	X	X	X	X			

	Open-Label Treatment (Period 3)					ETV	Post-Treatment Follow-Up (Period 4) ^x		
							Required Follow-Up Visits		As-Needed Follow-Up Visits
CRF Visit (V) Number	V8	V9	V10	V11	V12	ETVy	V801	V802	V803 ^z and onward
Weeks since Randomization	W16	W24	W28	W40	W52		LV + 4W	LV + 12W	LV + 24W
Study Days	112 ± 7d	168 ± 7d	196 ± 7d	280 ± 7d	364 ± 7d				
DLQI	X	X	X	X	X	X			
QIDS-SR16		X		X	X	X			
C-SSRS [§]	X	X	X	X	X	X	X	X	X
Self-Harm Supplement Form [§]	X	X	X	X	X	X	X	X	X
CAPP (genital subindex)					X	X			
Laboratory Tests									
HBV ⁿ			X	X	X			X	
Urine pregnancy test ^q	X	X	X	X	X	X			
Serum chemistry	X		X	X	X	X	X	X	X
Hematology	X		X	X	X	X	X	X	X
Fasting Lipid panel ^r			X	X	X	X			
Nonpharmacogenetic biomarker exploratory storage samples (serum, plasma, mRNA) ^s					X	X			
Immunogenicity testing ^{s,u}		X			X	X	X	X	
PK sample (trough) ^{s,v}		X			X	X	X	X	

Abbreviations: AE = adverse event; BP = blood pressure; BSA = body surface area; CAPP = Comprehensive Assessment of the Psoriasis Patient; CRF = case report form; C-SSRS = Columbia–Suicide Severity Rating Scale; d = days; DLQI = Dermatology Life Quality Index; DNA = deoxyribonucleic acid; ECG = electrocardiogram; ETV = early termination visit; FSH = follicle-stimulating hormone; GPSS = Genital Psoriasis Symptoms Scale; GPSIS = Genital Psoriasis Sexual Impact Scale; HBV = hepatitis B virus; HCV = hepatitis C virus; HIV = human immunodeficiency virus; IP = investigational product; LV = last visit; mRNA = messenger ribonucleic acid; mGPASI = modified Genital PASI; NRS = numeric rating scale; PASI = Psoriasis Area and Severity Index; PatGA-Genital = Patient’s Global Assessment of Genital Psoriasis; PK = pharmacokinetic; PPD = purified protein derivative; QIDS-SR16 = Quick Inventory of Depressive Symptomatology–Self Report (16 items); SDAL = Study Drug Administration Log; SFQ = Sexual Function Questionnaire; sPGA = static Physician’s Global Assessment; T4 = thyroxine; TB = tuberculosis; TSH = thyroid stimulating hormone; V = study visit; W = study week.

- a Demographics includes recording of year of birth, gender, ethnicity, and race.
- b Sociodemographics includes recording information on marital and sexual partner status.
- c One complete physical examination (excluding pelvic, rectal, and breast examinations) will be performed at screening. All physical examinations throughout the study should include a symptom directed physical as well as examination of heart, lungs, abdomen, and visual examination of the skin.
- d Patients who test positive for latent TB at screening, or who have a documented history of a positive TB test but do not have a documented history of at least 4 weeks of appropriate latent TB treatment, may be rescreened (Section 8.4.5). Additionally, patients who do not qualify at screening under exclusion criteria [34, 38, 39, 50] may be rescreened (1 time) as described in Section 5.3.
- e At baseline (Week 0) and Visit 7 (Week 12), BP and pulse should be measured prior to administration of the investigational product and again approximately 1 hour post-administration.
- f Habits include recording of caffeine, alcohol, and tobacco consumption.
- g Patients will record information including the date, time, and location of administration of investigational product (for treatment compliance), syringe number, who administered the investigational product, and the reason if investigational product was not fully administered in the SDAL.
- h As part of sPGA of Genitalia, the investigator will record on the eCRF (yes/no) whether psoriasis is present in women on labia minora, labia majora, and/or perineum and in men on penis (glans and/or shaft), scrotum, and/or perineum.
- i As part of mGPASI, the investigator will record on the eCRF (yes/no) if fissure, erosion, and/or ulcer are present in the genital area (defined as labia minora, labia majora, perineum for female patients and on the penis, scrotum, perineum for male patients).
- j As part of BSA, the investigator will record if psoriasis is present on the face, inframammary fold, axilla, scalp, nail, pubis, perianal region, gluteal cleft, and inguinal creases in the eCRF (yes/no) at baseline (Week 0), Week 4, 12, 24, 52, or ETV.
- k Patients should complete the scales in the following order: 1. GPSS, 2. GPSIS, and 3. SFQ. An e-diary will be used to collect these PROs up to Week 12 (V7); thereafter, patients will answer these questions only at scheduled study visits. At Week 12 (V7), patients will complete these scales on site before completion of any other assessments.
- l See Section 8.4.5 for detailed description of QuantiFERON®-TB Gold, T-SPOT®, and PPD testing.
- m A chest x-ray will be taken at screening unless one has been obtained within the past 6 months (provided the x-ray and/or report are available for review).

- ⁿ All patients will be tested for HBV at screening. Patients who are HBsAg+ at screening are excluded. Patients who are HBcAb+ at screening, regardless of other HBsAb status, will have serum HBV DNA obtained to be analyzed by the central laboratory. Patients that are found to be HBV DNA positive (detectable) at screening will be excluded from the trial. Patients that are HBcAb+ at screening and HBV DNA negative (undetectable) may be enrolled into the study with required HBV DNA monitoring every 3 to 4 months as outlined above in the Schedule of Activities during treatment and 12 weeks after the last dose of ixekizumab. If the result of the HBV DNA testing is positive, the patient must be discontinued from the study treatment, should continue safety follow up, and should receive appropriate follow-up medical care (refer to Section 8.4.9.2 for further information regarding the timing of discontinuation).
- ^o FSH test performed for women ≥ 40 and < 60 years of age who have had a cessation of menses for at least 12 months to confirm nonchildbearing potential (≥ 40 mIU/mL). FSH test will be performed centrally.
- ^p To be performed for females of childbearing potential only. Serum pregnancy test will be done at Visit 1 only and will be performed centrally.
- ^q To be performed for females of childbearing potential only. Patients will undergo urine pregnancy self-testing at home on a monthly basis during periods between scheduled visits through Week 52. During these intervisit periods, the site must call the patient each month to obtain her pregnancy test results. Additional urine pregnancy testing can be performed at the investigator's discretion. Patients determined to be pregnant will be discontinued from treatment and will no longer be administered investigational product (see Section 7.1).
- ^r For the fasting lipid profile patients should not eat or drink anything except water for 12 hours prior to test. (For ETV: [1] If ETV is planned, then fasting lipid profile should be performed, and [2] if ETV is not planned and patient is not fasting, the lipid profile should not be performed.)
- ^s Samples will be collected as allowed by local regulations.
- ^t If the DNA sample is not collected at Visit 2 (Week 0), it can be collected at Visit 3 (Week 4).
- ^u Immunogenicity samples may also be analyzed for ixekizumab serum concentration to facilitate in the interpretation of the immunogenicity data. In addition, a blood sample will be collected, when possible, for any patient who experiences a potential systemic allergic/hypersensitivity reaction during the study as judged by the investigator (Section 8.4.6).
- ^v At visits where dosing is scheduled, PK samples will be collected prior to administration of investigational product (Section 8.5).
- ^w Swab from labia majora for women and glans penis for men.
- ^x All patients receiving investigational product must enter into Period 4 and complete through Visit 802. Patients may be followed beyond Visit 802 for continued monitoring of their neutrophil counts or for other safety reasons.
- ^y If a patient discontinues study treatment early, the patient will complete the ETV and then enter the Post-Treatment Follow-Up Period.
- ^z This visit will only occur if a patient's neutrophil counts have not returned to the criteria defined in Section 8.4.9.1 or for other safety reasons.
- [§] A Self-Harm Follow-Up Form is to be completed for each discrete self-harm event identified on the C-SSRS and the Self-Harm Supplement Form.

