Appendix 3. Clinical Laboratory Tests

Hematology^{a,b}

Hemoglobin
 Hematocrit
 Erythrocyte count (RBC)
 Mean cell volume (MCV)
 Mean cell hemoglobin concentration (MCHC)
 Leukocytes (WBC)
 Platelets

Absolute counts of:

Neutrophils, segmented
 Neutrophils, juvenile (bands)
 Lymphocytes
 Monocytes
 Eosinophils
 Basophils

Other Tests^a

Human immunodeficiency virus antibody (HIV)^c
 Hepatitis B Surface antigen (HBsAg)^{d,e}
 Anti-Hepatitis B Surface antibody (HBsAb)^{d,e}
 Anti-Hepatitis B Core antibody (HBcAb)^{d,e}
 Anti-Hepatitis C antibody^{c,d}
 HBV DNA^{c,f}
 Thyroid-stimulating hormone (TSH) and Free T4
 Ixekizumab serum concentration
 Exploratory storage samples (serum, plasma, DNA, & mRNA)

Purified Protein Derivative (PPD)^g

Serum Chemistry^{a,b}

Sodium
 Potassium
 Bicarbonate
 Chloride
 Phosphorus
 Total bilirubin
 Direct bilirubin
 Alkaline phosphatase
 Alanine aminotransferase (ALT/SGPT)
 Aspartate aminotransferase (AST/SGOT)
 Blood urea nitrogen (BUN)
 Uric acid
 Creatinine
 Calcium
 Glucose
 Albumin
 Cholesterol (total)
 Total protein

Triglycerides
 Gamma-Glutamyl Transferase (GGT)

Fasting Lipid Panel^{a,h}
 Low Density Lipoprotein (LDL-C)
 High Density Lipoprotein (HDL)
 Very Low Density Lipoprotein (VLDL)

Pregnancy Test (serum and urine)ⁱ

Follicle-stimulating hormone (FSH)^j

Clinical Safety Laboratory Tests

Abbreviations: Ab = antibody; DNA = deoxyribonucleic acid; HBcAb = anti-hepatitis B core antibody; HBsAb = anti-hepatitis B surface antibody; HBsAb+ = positive for anti-hepatitis B surface antibody; HBsAg- = negative for hepatitis B surface antigen; HBV = hepatitis B virus; LDL-C = low density lipoprotein calculated; mRNA = messenger ribonucleic acid; RBC = red blood cells; SGOT = serum glutamic oxaloacetic transaminase; SGPT = serum glutamic pyruvic transaminase; T4 = thyroxine; TB = tuberculosis; WBC = white blood cells.

- a Assayed by sponsor-designated laboratory.
- b Unscheduled blood chemistry and hematology panels may be performed at the discretion of the investigator.
- c See exclusion criteria (Section 5.2).
- d Test required at Visit 1 only to determine eligibility of patient for the study.
- e Quantitative HBsAb testing will be done in those patients who are HBsAg-, HBcAb+, and HBsAb+ at screening.
- f Refer to hepatitis B monitoring (Section 8.4.9.2).
- g In countries where the QuantiFERON®-TB Gold test or T-SPOT® is available, it may be used instead of the PPD TB test and may be performed locally.

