6.15.4. Clinical Laboratory Evaluation

Clinical laboratory assessments include hematology, serum chemistry, urinalysis, and safety related immune markers such as neutrophil counts. Continuous laboratory tests will be summarized as changes from baseline to last observation for patients who have both baseline and at least one post-baseline result for Period 2, Period 3, and Period 4, respectively:

- The scheduled visits/measurements will be included. The unscheduled visits and the repeated measurements taken at the same visit will be excluded.
- Both international system of unit (SI) and conventional unit will be summarized when different.
- For the safety population in the Blinded Treatment Period (Period 2), the comparisons between treatment groups will be conducted using an ANCOVA method with treatment group and baseline value in the model.
- Data will be analyzed based on original scale.

Laboratory test observed values at each visit (starting at baseline) and change from baseline to each scheduled visit, respectively, will be displayed in box plots for patients who have both a baseline and at least one post-baseline result. These box plots will be used to evaluate trends over time and to assess a potential impact of outliers on central tendency summaries.

The scheduled visits/measurements will be included. The unscheduled visits and the repeated measurements taken at the same visit will be excluded.

- The displays with both SI and conventional units will be provided when different.
- The following summary statistics will be included as a table below the box plot: number of patients with a baseline and at least one post-baseline result, mean, standard deviation, minimum, Q1, median, Q3, and maximum.
- Data will be summarized based on original scale.
- On the box plots of the laboratory test observed values, the lines of the reference ranges/limits (by using the large clinical trial population based reference limits, that is, Lilly reference ranges) will be added. In cases where limits vary across age and gender, the lowest of the high limits and the highest of the low limits will be used.

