- The number and percentage of patients with a treatment-emergent or follow-up emergent abnormal, high, or low for laboratory tests will be summarized by treatment group for each study period. The comparisons between treatment groups will be conducted using Fisher's exact test for the safety population in the Blinded Treatment Period (Period 2). All scheduled, unscheduled and repeated measurements taken at the same visit will be included.
- In general, large clinical trial population based reference limits (that is, Lilly reference ranges) will be used to define the low and high limits since it is generally desirable for

limits used for analyses to have greater specificity (identify fewer false positive cases) than reference limits used for individual subject management. In the case when the reference limits based on the large clinical trial population is not available for a laboratory measure, performing lab reference ranges will be used. Alanine aminotransferase (ALT), aspartate aminotransferase (AST), total bilirubin, and alkaline phosphatase (ALP), neutrophils, leukocytes, platelets and lymphocytes, will not be included in the treatment-emergent abnormal, high, or low summary as a separate analysis addressing the risk of liver injury is described in Section 6.15.3.1 in which performing lab reference ranges are used.

- Note that the ranges are defined by a lower limit of normal (LLN) and an upper limit of normal (ULN). A result that is greater than or equal to the LLN and less than or equal to the ULN is considered to be within the normal ranges.
- For categorical laboratory tests:
 - Treatment-emergent abnormal value is defined as a change from normal at all baseline visits to abnormal at any time post-baseline during the Blinded Treatment Period.
 - Treatment-emergent abnormal value is defined as a change from normal at baseline to abnormal at any time post-baseline during the Open-label Treatment Period.
 - Follow-up emergent abnormal result is defined as a change from normal at baseline to abnormal at any time during the follow-up period.
- For continuous laboratory tests:
 - Treatment-emergent high value is defined as a change from a value less than or equal to the ULN at all baseline visits to a value greater than the ULN at any time post-baseline during the Blinded Treatment Period.

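### Triglycerides, total cholesterol and glucose are drawn at some visits with no fasting requirement but compared with fasting-visit baselines, so Period 3 emergent-high rates and Period 4 rates and mean changes can be biased upward

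*Protocol*

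**What the plan says.** **Panels.** Protocol Appendix 3 lists glucose and total cholesterol under serum chemistry. "Triglycerides" comes next to GGT and before the fasting panel's heading, so by list order it is also chemistry. The fasting panel names only LDL-C, HDL and VLDL.

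**Fasting rule.** Footnote r of the Schedule of Activities (Protocol Appendix 2) and footnote h of Appendix 3 tie the 12-hour fast to the lipid profile. Footnote r adds, for an early termination visit (ETV), "if ETV is not planned and patient is not fasting, the lipid profile should not be performed". No fasting rule is given for chemistry. Appendix 3 footnote b allows unscheduled chemistry panels.

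**Schedule.** The "Fasting Lipid panel" row is marked at Visits 2, 5, 7, 10, 11, 12 and ETV. Chemistry is marked at all of these and also at Visits 1, 8, 801, 802 and 803.

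**Analysis.** SAP 6.15.4 states "Continuous laboratory tests will be summarized as changes from baseline to last observation", separately for Periods 2, 3 and 4, from scheduled measurements only. By-visit box plots use the same restriction. For emergent abnormal, high and low results, however, "All scheduled, unscheduled and repeated measurements taken at the same visit will be included". Eight hepatic and hematology analytes are left out of that emergent summary. Lipids and glucose are not among them. Nothing in the section refers to fasting status.

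**Baselines (SAP 6.1.2).** Period 3 uses the last value up to Visit 7, before the first open-label injection. Period 4 uses the last value up to Visit 12 or ETV. The Period 2 baseline period starts at Visit 1.

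**The concern.** The protocol takes care not to collect an unfasted lipid panel at an unplanned ETV, yet triglycerides and total cholesterol are still measured at that visit through chemistry. The same holds at every chemistry visit outside the fasting schedule. The SAP then pools values with and without a fasting requirement against a baseline that is usually fasting.

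In Period 4 the fasting instruction ends just as treatment ends, so a difference in fasting state coincides with the period being described. In Period 3 a single value above the limit at Visit 8 is enough to classify a patient as emergent high. Neither period has a concurrent untreated arm that would show the artefact. A reader of the long-term safety tables could take a meal effect for a change in triglycerides or glucose during or after treatment.

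**Working it through.** The plan states no figure on this point, so there is nothing to reproduce. The check sets the two schedule rows against the SAP definitions and then illustrates the size.

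**1. Scheduled post-baseline chemistry draws**

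| Period | Draws | No fasting requirement |
|---|---|---|
| 2 | V5, V7 | 0 of 2 |
| 3 | V8, V10, V11, V12 | 1 of 4 (V8) |
| 4 | V801, V802 (V803 if needed) | 2 of 2 (3 of 3 with V803) |

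An unplanned ETV and unscheduled draws may also be unfasted.

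**2. Mean change to last observation.** Let d be the food effect and q the share of patients whose last treatment-period value is V8 or an unfasted ETV.
- Period 3 shift = q × d. Completers end at V12, a fasting visit. For q of 5% to 20% the shift is 0.05d to 0.20d. Only the V8 by-visit display carries the full d.
- Period 4 shift is about (1 − q) × d, because an unfasted ETV also supplies an unfasted baseline. For q of 0% to 20% it is 1.00d to 0.80d.

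**3. Emergent-high rate, independent draws.** Let pf and pn be the assumed chances of a high value at a fasting and an unfasted draw.
- Period 3: 1 − (1 − pf)³(1 − pn), against 1 − (1 − pf)⁴ if all draws were fasting.
- Period 4: 1 − (1 − pn)², against 1 − (1 − pf)².

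With pf = 5% and pn = 10%, Period 3 is 1 − 0.95³ × 0.90 = 22.8% against 18.5%. Period 4 is 1 − 0.90² = 19.0% against 9.8%. Over pn = 1.5 to 3 times pf:

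| pf | Period 3, all fasting | Period 3, as scheduled | Period 4, all fasting | Period 4, as scheduled |
|---|---|---|---|---|
| 2% | 7.8% | 8.7–11.5% | 4.0% | 5.9–11.6% |
| 5% | 18.5% | 20.7–27.1% | 9.8% | 14.4–27.8% |
| 10% | 34.4% | 38.0–49.0% | 19.0% | 27.8–51.0% |

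With pn = pf there is no change.

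**4. Emergent-high rate, correlated draws, triglycerides only.** Assume log-normal values with SD 0.45 between patients and 0.22 within, and condition on a normal fasting baseline. Let f and n be a patient's chances of a normal value when fasting and unfasted, averaged over patients. The Period 3 rate is 1 − E[f⁴n]/E[f] and the Period 4 rate is 1 − E[f n²]/E[f]. With 15% of fasting values high and a 20% food effect, Period 3 goes from about 16% to 21% and Period 4 from about 11% to 23%. With 25% high and a 30% effect, Period 3 goes from about 24% to 35% and Period 4 from about 17% to 40%.

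**5. Visit 1 works the other way.** Period 2 emergent high requires normal values at all baseline visits, so a high V1 value removes the patient from the at-risk set. In the 15% high, 20% effect case, 85% are normal at V2 alone, 79% at two fasting visits, and 72% when V1 is unfasted. Food accounts only for the last step.

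**The case against.** A reader might infer that all long-term mean changes and rates for these analytes rise by construction. The documents do not support that, for several reasons, and each of them stands.

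- Period 3 change to last observation normally ends at Visit 12, a fasting visit, and is largely unaffected.
- The SAP does not use every value in every analysis. Unscheduled and repeat values are excluded from mean change and box plots and enter only the emergent summary.
- The plan does not say that patients have eaten at Visits 8 or 801 to 803. It only sets no fasting requirement there.
- Not every Period 4 baseline is fasting, because an unplanned ETV can supply an unfasted one.
- Upward bias needs a food effect. The documents give none, and the correlated-draw illustration covers triglycerides only. The SAP's preferred reference limits, chosen for specificity, are not stated, so the assumed share of high values cannot be checked.

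The consequence is also limited. The primary safety comparison is Period 2, whose scheduled post-baseline chemistry falls on fasting visits. The Visit 1 effect precedes randomization and should be similar in both arms. Periods 3 and 4 have no between-group test, metabolic change is not an adverse event of special interest, and the Visit 10, 11 and 12 displays remain readable.

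These points do not answer the Period 4 comparison for completers, or the counting of Visit 8 as emergent against a fasting baseline.

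**Conclusion.** The concern holds for four outputs: the Period 3 emergent-high rate, the Visit 8 by-visit display, the Period 4 emergent-high rate, and the Period 4 change to last observation. In Period 4 every scheduled draw is affected, and for completers the mean change carries the whole food effect. In Period 3 one draw in four is affected.

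The size rests on assumptions from outside the documents. Over the ranges shown, Period 3 rates rise modestly to appreciably, while Period 4 rates can double or more. The bias is zero for any analyte that food does not raise, and it may differ between the three. Placing triglycerides in chemistry rests on list order in Appendix 3.

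It would go too far to read this as undermining the randomized safety comparison or making Period 3 uninterpretable. It is a fasting-state confound in descriptive long-term summaries, worth correcting because the correction is cheap.

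**What to change.** In SAP 6.15.4, for triglycerides, total cholesterol and glucose:

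- Base the emergent-high and change-from-baseline analyses on visits with the fasting panel: Visits 2, 5, 7, 10, 11, 12 and a planned, fasting ETV.
- Use Visit 2 alone as the Period 2 baseline.
- Summarize values from Visits 8 and 801 to 803, a non-fasting ETV and unscheduled draws separately, labelled as fasting not required. Do not count them as emergent against a fasting baseline.

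The cost is SAP wording and a visit filter for three analytes, with no change to sampling. The Visit 8 value leaves the main emergent count, and the Period 4 summary for these analytes becomes a labelled descriptive display. No data are dropped from reporting.
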